NCT03349996 Unique Protocol ID: ID3-20170704**PROTOCOL SYNOPSIS: BELSTREAM study**

| | | |
|---------------------------|--|---|
| Title | Belgian Physician-Initiated Trial Investigating the Lifestream Peripheral Stent Graft System for the treatment of complex TASC C and D iliac lesions | |
| Objective | The objective of this clinical investigation is to evaluate, in a controlled setting, the long-term (up to 60 months) safety and efficacy of the Lifestream Peripheral Stent Graft System (Bard) in clinical settings post CE-certification when used according to the indications of the IFU. | |
| Methodology | Prospective, multi-center, physician-sponsored clinical study | |
| Enrollment | 70 subjects | |
| Primary Endpoint | Efficacy endpoint | The primary endpoint of the study is primary patency at 12 months , defined as a target lesion without a hemodynamically significant stenosis on duplex ultrasound (>50%, systolic velocity ratio greater than 2.5) and with freedom from Target Lesion Revascularization (TLR) within 12 months. TLR is defined as a repeated intervention to maintain or re-establish patency within the region of the treated arterial vessel plus 5mm proximal and distal to the treated lesion edge. |
| | Safety endpoint | The primary safety endpoint of the study is the freedom of periprocedural Serious Adverse Events (SAEs), defined according to ISO 14155:2011 as any clinical event that is fatal, life-threatening, or judged to be severe by the investigator; resulted in persistent or significant disability; necessitated surgical or percutaneous intervention; or required prolonged hospitalization. |
| Secondary Endpoint | 1. | Primary patency rate at 1-, 6-, 24-, 36-, 48- and 60 month follow-up. Patients that present without a hemodynamically significant stenosis at the target area on duplex ultrasound (>50%, systolic velocity ratio greater than 2.5) and without prior TLR are defined as being primary patent at the given follow-up. |
| | 2. | Stent graft occlusion rate at pre-discharge, 1-, 6-, 12-, 24-, 36-, 48-, and 60-month follow-up. |
| | 3. | Ankle Brachial Index (ABI) at 1-, 6-, 12-, 24-, 36-, 48- and 60 month follow-up compared with the baseline ABI. |
| | 4. | Amputation rate at 1-, 6-, 12-, 24-, 36-, 48- and 60 month follow-up, defined as any amputation above the knee. |
| | 5. | Technical success, defined as the ability to achieve final residual angiographic stenosis no greater than 30%. |

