| 19. | Perforation at the angioplasty site evidenced by extravasation of contrast medium |
| 20. | Patients with a history of prior life-threatening contrast medium reaction |
| 21. | Patients with uncorrected bleeding disorders |
| 22. | Female patient with child bearing potential not taking adequate contraceptives or currently breastfeeding |
| 23. | Life expectancy of less than twelve months |
| 24. | Any planned surgical intervention/procedure within 30 days of the study procedure |
| 25. | Any patient considered to be hemodynamically unstable at onset of procedure |
| P.I. | [name], ZNA Campus Stuivenberg, Antwerp, Belgium |
| Study conduct | The study will be conducted in accordance with the Declaration of Helsinki and ISO 14155:2011, and comply with requirements regarding Ethics Committees and any other applicable regulations |
| Participating sites | 
 A.Z. Groeninge, Kortrijk, Belgium: [name]Z. Sint-Blasius, Dendermonde, Belgium: [name] Hospital, Bonheiden, Belgium: [name]L.V. Hospital, Aalst, Belgium: [name]Z. H.H., Tienen, Belgium: [name]O.L., Genk, Belgium: [name]N.A. Stuivenberg, Antwerpen, Belgium: [name] |

Table 1. Study Investigations

| Time | | Tests and Procedures |
|---|----------------------|--|
| Pre-Procedure (up to 24 hours before procedure, unless otherwise noted.) | 1. 2. 3. 4. | Medical History Medication Registration Physical Exam Rutherford Categorization and ABI |
| Procedure | 1. 2. 3. 4. | Angiography, pre-procedure Study inclusion Intervention Rutherford Categorization and ABI |
| One day Post-Procedure | 1. 2. 3. | Medication Registration Physical Examination Rutherford Categorization and ABI |
| One month Follow-up (\pm 7 days) | 1. 2. 3. 4. | Medication Registration Physical Examination Rutherford Categorization and ABI Colour Flow Doppler Ultrasound |
| Six month Follow-up (\pm 30 days) | 1. 2. 3. 4. | Medication Registration Physical Examination Rutherford Categorization and ABI Colour Flow Doppler Ultrasound |
| One year Follow-up (\pm 30 days) | 1. 2. 3. 4. | Medication Registration Physical Examination Rutherford Categorization and ABI Colour Flow Doppler Ultrasound |
| Two year Follow-up (730 ± 30 days) | 1. 2. 3. 4. | Medication Registration Physical Examination Rutherford Categorization and ABI Colour Flow Doppler Ultrasound |

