| Three year Follow-up (1095 ± 30 days) | 1. 2. 3. 4. | Medication Registration Physical Examination Rutherford Categorization and ABI Colour Flow Doppler Ultrasound |
| Four year Follow-up (1460 ± 30 days) | 1. 2. 3. 4. | Medication Registration Physical Examination Rutherford Categorization and ABI Colour Flow Doppler Ultrasound |
| Five year Follow-up (1825 ± 30 days) | 1. 2. 3. 4. | Medication Registration Physical Examination Rutherford Categorization and ABI Colour Flow Doppler Ultrasound |

- Statistical Analysis Plan (SAP)

Descriptive data summaries will be used to present and summarize the collected data. For categorical variables (e.g. Gender) frequency distributions and cross tabulations will be given. For numeric variables (e.g. Patient age) minimum, maximum, mean, median and standard deviation will be calculated. For all variables a 95% confidence interval for the relevant parameters of the underlying distribution will be calculated. For all time-dependent events life-tables will be calculated using the Kaplan Meier estimate method, for a period starting on the date of the procedure up to and including the 60-month follow-up visit. Stratification to pre-procedural risk factors, Rutherford and lesion criteria will be performed and the log rank test will be used to compare between the different outcomes, associated p-values < 0.05 are defined as significant.

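### The SAP uses Kaplan-Meier for every event to 60 months with no rule for death; above-knee amputation, and occlusion alongside it, should also be given as cumulative incidence

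*Combined protocol and SAP*

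**What the plan says.** The Statistical Analysis Plan is a single paragraph. Its only time-to-event estimator is given in the sentence "For all time-dependent events life-tables will be calculated using the Kaplan Meier estimate method", applied "for a period starting on the date of the procedure up to and including the 60-month follow-up visit". It contains no censoring rule, does not say what happens to a patient who dies, and names no competing-risk method.

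Two of the endpoints in the Protocol Synopsis to which this may apply are:

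- Secondary Endpoint 2: "Stent graft occlusion rate at pre-discharge, 1-, 6-, 12-, 24-, 36-, 48-, and 60-month follow-up".
- Secondary Endpoint 4: "Amputation rate at 1-, 6-, 12-, 24-, 36-, 48- and 60 month follow-up, defined as any amputation above the knee".

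Neither includes death. Mortality is not a listed endpoint; fatal events appear only within the definition of periprocedural serious adverse events. The one exclusion on expected survival is item 23: "Life expectancy of less than twelve months".

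Target lesion revascularization (TLR) is defined only as a component of primary patency ("TLR is defined as a repeated intervention to maintain or re-establish patency within the region of the treated arterial vessel"). No separate TLR rate is listed.

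**The concern.** Follow-up runs for five years, and the entry criteria screen out only patients not expected to survive the first. Some deaths before 60 months are therefore foreseeable. A patient who dies without an amputation or occlusion can no longer have one. Kaplan-Meier recognises only an event or a censored time, so if death is not counted as an event it would ordinarily be entered as censoring. 1-KM then estimates the risk in a population in which nobody dies, under independent censoring. That is at or above the proportion of patients who have the event, and strictly above it once any event occurs after a death.

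The stated objective is long-term safety and efficacy up to 60 months, so the late time points matter. A reader who takes a 5-year amputation figure as the share of patients who lost a leg would be reading too high a number. The confidence interval around 1-KM would not reveal it, and no mortality endpoint is planned that would help to interpret it.

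**Working it through.** The plan states no figure on this point: enrollment of 70 comes without a power calculation, an expected event rate or a mortality rate. There is nothing to reproduce, and the check compares the two estimators under assumed rates.

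**Inputs.** From the documents: 70 subjects, a 60-month horizon, Kaplan-Meier for all time-dependent events. Assumed: constant, independent yearly hazards, h = 0.01 to 0.06 for the event and d = 0.03 to 0.08 for death. These death hazards imply 5-year mortality of 1 - exp(-0.15) = 13.9% to 1 - exp(-0.40) = 33.0%.

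**Formulas at 5 years.**

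- Kaplan-Meier with deaths censored: 1-KM = 1 - exp(-5h).
- Cumulative incidence with death competing: CIF = h/(h+d) × (1 - exp(-5(h+d))).
- Approximate 95% half-width with all 70 followed: 1.96 × √(p(1-p)/70), with p = 1-KM.

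**One case in full**, h = 0.04 and d = 0.05: 1-KM = 1 - exp(-0.20) = 18.13%. CIF = 0.04/0.09 × (1 - exp(-0.45)) = 0.4444 × 0.3624 = 16.11%. The excess is 2.02 points.

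| Event/yr | Death/yr | 1-KM | CIF | Excess (points) | Half-width at n=70 |
|---|---|---|---|---|---|
| 1% | 3% | 4.88% | 4.53% | 0.35 | 5.0 |
| 2% | 5% | 9.52% | 8.44% | 1.08 | 6.9 |
| 4% | 5% | 18.13% | 16.11% | 2.02 | 9.0 |
| 4% | 8% | 18.13% | 15.04% | 3.09 | 9.0 |
| 6% | 8% | 25.92% | 21.57% | 4.34 | 10.3 |

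(Differences are taken before rounding.) The first and last rows are the extremes of the grid, so the excess runs from about 0.3 to 4.3 points. That is 0.2 to 3.0 patients of 70, or 7% to 21% of the cumulative incidence.

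**Timing of events.** Constant hazards are unfavourable to Kaplan-Meier, because early events leave less time for death to intervene. With two thirds of the cumulative event hazard in year 1, a 5-year 1-KM of 20% and 5-year mortality of 20%, the excess is 1.1 points. With constant hazards and the same inputs it is 2.0.

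**12 months.** Put h = -ln(1-q) and d = -ln(1-m), with q the 1-year 1-KM risk and m the 1-year mortality, over one year. At q = 15% and m = 8%, h = 0.1625, d = 0.0834 and CIF = 0.661 × (1 - exp(-0.2459)) = 14.41%. The excess is 0.6 points, the largest found for risks up to 15% and mortality up to 8%.

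**The case against.** Several points on the other side stand.

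- **The plan does not say that deaths are censored.** A reader might infer that it does. The text is silent, and censoring is what ordinary use of the named method would produce. What can be seen on the page is a missing rule.
- **Occlusion and amputation may not be meant as Kaplan-Meier estimates.** They are worded as rates at visits, and the SAP also provides frequency distributions for categorical variables. But if they are simple proportions, the plan leaves open how deaths enter the denominator, so a sentence is needed either way.
- **For a device, death-censored Kaplan-Meier is a legitimate durability measure.** It is too high only as a statement about the share of patients affected. This is a good argument for occlusion, which is also a loss of patency and needs to be readable on the same scale as patency. It is weak for above-knee amputation, which is a patient outcome.
- **TLR.** A reader might add a 5-year TLR rate to the affected figures. The documents list none; the point reaches TLR only if it is reported separately.
- **The log-rank tests.** One might infer that comparisons across strata, where "associated p-values < 0.05 are defined as significant", become uninterpretable when mortality differs. They do not: with deaths censored, the log-rank test validly compares cause-specific hazards.
- **Size.** The excess rests on assumed rates and lies below the approximate 95% half-width in every row of the table. It is nevertheless systematic, in one direction and avoidable.

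**Conclusion.** The concern holds as a modest one. The SAP names a single estimator for all time-dependent events and has no rule for death. Applied in the ordinary way, it would overstate the share of patients with an above-knee amputation or a stent graft occlusion by 60 months. The size cannot be derived from the documents. The range of about 0.3 to 4.3 points depends on the assumed constant, independent hazards, and roughly halves if most events come in year 1. With 70 patients this is usually smaller than sampling error, and for the 12-month primary endpoint it is negligible.

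The documents do not support saying that the long-term rates are known to be overstated, or that Kaplan-Meier is wrong for every endpoint. This is a cheap improvement to the plan, not a flaw that threatens its conclusions.

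**What to change.** Add to the SAP, for each event, a sentence on how death is handled. Then:

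- **Above-knee amputation:** report the Aalen-Johansen cumulative incidence, with death as a competing event and a 95% CI.
- **Stent graft occlusion, and TLR only if it is reported separately:** report the cumulative incidence alongside the Kaplan-Meier estimate, so that occlusion can still be read against patency.
- **Primary patency:** keep Kaplan-Meier, labelled as censoring deaths with a patent lesion.
- **Log-rank comparisons:** no change.

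The cost is a few sentences, dates of death and one standard routine. The small downside is two estimates to present and explain for occlusion.

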| | 6. | Clinical success at follow-up is defined as an improvement of Rutherford classification at 1-, 6-, 12-, 24-, 36-, 48- and 60 -month follow-up of one class or more as compared to the pre-procedure Rutherford classification. |
| Inclusion Criteria | General inclusion criteria | |
| | 1. | Corresponding to the CE-mark indications/contra-indications and according to the current medical guidelines for minimally invasive peripheral interventions. |
| | 2. | Patient presenting with a stenotic or occlusive lesion at the iliac arteries suitable for stenting (on indication for primary stenting, based on the discretion of the investigator) |
| | 3. | Patient presenting a score from 2 to 4 following Rutherford classification |
| | 4. | Patient is willing to comply with specified follow-up evaluations at the specified times for the duration of the study |
| | 5. | Patient is >18 years old |

| | |
|--|--|
| | 
6. Patient (or their legal representative) understands the nature of the procedure and provides written informed consent, prior to enrolment in the study
 
7. Patient is eligible for treatment with the Lifestream Peripheral Stent Graft System (Bard)
 |
| Angiographic inclusion criteria | |
| | 
1. The target lesion is either a modified TASC-II class C or D lesion with one of the listed specifications:
 
 ○ Type C lesions 
 ● Bilateral Common Iliac Artery occlusions ● Bilateral External Iliac Artery stenoses 3–10 cm long not extending into the Common Femoral Artery ○ Type D lesions 
 ● Unilateral occlusions of both Common Iliac and External Iliac Artery ● Diffuse disease involving the aorta bifurcation ● Bilateral occlusions of External Iliac Artery |
| | 
2. The target lesion has angiographic evidence of stenosis or restenosis post PTA >50% or occlusion which can be passed with standard guidewire manipulation
 |
| | 
3. There is angiographic evidence of a patent Common and Deep Femoral Artery
 |

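### The SAP declares any log-rank p-value below 0.05 between strata significant, yet leaves the risk factors and groupings open and does not call the tests exploratory

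*Combined protocol and SAP*

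**What the plan says.** The Statistical Analysis Plan (SAP) section is a single paragraph. It opens descriptively: "Descriptive data summaries will be used to present and summarize the collected data". It then promises intervals: "For all variables a 95% confidence interval for the relevant parameters of the underlying distribution will be calculated". For event data, "For all time-dependent events life-tables will be calculated using the Kaplan Meier estimate method", and the period covered is "for a period starting on the date of the procedure up to and including the 60-month follow-up visit". The paragraph closes with the comparisons. It names the strata first: "Stratification to pre-procedural risk factors, Rutherford and lesion criteria will be performed". The decision rule for comparing them follows in the same sentence: "the log rank test will be used to compare between the different outcomes, associated p-values < 0.05 are defined as significant".

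The categories that could serve as strata appear only as eligibility criteria in the synopsis:

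- **Rutherford (general inclusion criteria):** "Patient presenting a score from 2 to 4 following Rutherford classification", which allows three classes.
- **Lesion (angiographic inclusion criteria):** "The target lesion is either a modified TASC-II class C or D lesion with one of the listed specifications". Two Type C and three Type D specifications follow, so there are five sub-types.

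The documents describe no comparator arm. The log-rank tests can therefore only compare strata within the one treated group, although the sentence speaks of comparing outcomes.

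**The concern.** The last sentence of the SAP is a decision rule: a p-value below the threshold is significant. The set of tests to which it applies is open.

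- The baseline risk factors are not listed. Table 1 collects medical history, medication, physical examination and ABI before the procedure, and any of these could supply a factor.
- The SAP does not say whether lesions are split into C v D or into the five sub-types.
- It does not say which time-dependent events are tested. Testing all of them is the natural reading, but it is not explicit.
- Nothing caps the number of tests, adjusts for it, or marks the results as exploratory.

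Follow-up lasts five years, so factors and groupings could be settled after outcomes are known. At stake is a report that one subgroup of 70 subjects did significantly better or worse than another, with no sign of how many comparisons were tried.

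**Working it through.** **Inputs from the documents.** Per-test threshold 0.05 (SAP); named strata are risk factors (plural), Rutherford and lesion criteria (SAP); 70 subjects (synopsis, Enrollment).

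**Assumed, because the documents give no figure.** The number of tests k beyond the literal minimum, event rates, stratum sizes and the correlation between factors.

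**Starting point.** The only stated figure is the 0.05 threshold. For one test, 1 − 0.95¹ = 5%, as expected. The plan states no family-wise error rate to reproduce.

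**Smallest literal count.** At least two risk factors + Rutherford + lesion criteria = 4 tests, counting Rutherford and lesion criteria as one test each on one outcome.

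**Chance of at least one false significant result**, with no true effects and independent tests: 1 − 0.95^k. The expected number of false results is 0.05k.

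| k | Reading | Chance | Expected number |
|---|---|---|---|
| 4 | literal minimum, one outcome | 1 − 0.8145 = 18.5% | 0.20 |
| 8 | same four factors, two outcomes (assumed) | 33.7% | 0.40 |
| 10 | assumed | 40.1% | 0.50 |

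**Dependence.** Whatever the correlation, four tests each at 5% cannot exceed 4 × 0.05 = 20%. If all four were perfectly correlated, the chance would be 5%. Log-rank simulations with n = 70, no true effects, assumed patency loss of 10%, 20% or 40%, and factor correlation from 0 to 0.5 gave 12.9–15.8% for three factors (formula 14.3%) and 34.1–40.4% for ten (formula 40.1%). The formula is therefore a fair guide over that range.

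**Rare events.** With 35 v 35 subjects, the simulated per-test error was about 3.5% at an assumed event rate of 5%, and 0.6% at 2%. Adding rare outcomes to the set of tests therefore adds little.

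**Can a hazard ratio be relied on in each stratum?** Split 70 subjects equally over five lesion sub-types, 14 each, with 10% patency loss (both assumed). A given stratum has no event with probability 0.9¹⁴ = 23%. At least one of five has none with probability 1 − (1 − 0.229)⁵ = 73%. An ordinary hazard ratio involving such a stratum has no finite estimate.

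**The case against.** The strongest reply is that little depends on these tests. The study has no control arm and states no hypothesis or error budget, and the SAP is mostly descriptive. Without a confirmatory family, no family-wise error rate has been promised. This stands as a limit on the weight of the point. It does not remove it, because the opening descriptive sentence is not tied to the log-rank tests, and the same paragraph gives those tests a significance rule.

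It is also fair to say that two of the three named factors come with natural categories. Rutherford is already a class variable, and stratifying by class 2, 3 and 4 is the plain reading. A reader might infer that the plan invites trying 2 v 3–4, 2–3 v 4 and all three classes. In simulation with assumed class proportions, reporting whichever succeeds raises the 5% error for Rutherford to 9–11%. But no section proposes those pooled groupings, so that figure is not a property of the plan. For lesions there is a real choice, since the protocol supplies both C v D and sub-types and the SAP picks neither. Only the risk factors are wholly open.

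Finally, counts of 10 or more have no anchor in the documents and serve only to show the direction.

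**Conclusion.** The point holds as a modest one. As written, the plan would allow subgroup differences to be called significant with an overall false-positive chance well above 5%: about 19% at the literal minimum of four tests, if they are independent and there are no true effects. The chance is higher if more factors or outcomes are tested; 40% is an illustration for an assumed 10 tests.

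A reader might infer that the primary result is compromised or that a formal multiplicity correction is required. The documents support neither. The 12-month primary patency estimate does not pass through these tests, and for secondary subgroup comparisons in a study with no stated hypothesis, an exploratory label and a fixed list are enough. The harm is limited to over-reading secondary subgroup results.

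**What to change.** In the SAP section:

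1. Replace the clause that defines significance with a statement that the log-rank comparisons between strata are exploratory and their p-values nominal. In the same edit, say that strata are compared on each outcome.
2. List the risk factors and groupings in advance: Rutherford by class 2, 3 and 4; lesions by C v D or by sub-type, with one chosen. Name primary patency as the main outcome for these comparisons.
3. Report the number of comparisons made, with Kaplan-Meier estimates and 95% confidence intervals for each stratum. Give hazard ratios only where every stratum has events.

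The SAP already promises 95% confidence intervals. Unadjusted intervals do not control multiplicity, so the label and the list do the main work.

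The cost is SAP wording and a decision on which factors matter, with no change to sample size, visits or data collection. Any hazard ratios would be an addition, since the SAP plans no hazard model. The downside is that no subgroup result can be called significant.

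### The SAP's log-rank p < 0.05 rule has no safeguard for endpoints with few events and small strata, where the chi-square p-value is unreliable

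*Combined protocol and SAP*

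**What the plan says.** The Statistical Analysis Plan is one paragraph. On event data it states: "For all time-dependent events life-tables will be calculated using the Kaplan Meier estimate method", from the procedure to the 60-month visit. It continues: "Stratification to pre-procedural risk factors, Rutherford and lesion criteria will be performed". Then "the log rank test will be used to compare between the different outcomes, associated p-values < 0.05 are defined as significant". The trial has one cohort, so I read this as comparing Kaplan-Meier curves between strata.

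The SAP gives no stratum sizes, no number of groups per comparison, no expected event rates and no minimum event count. It names no exact or permutation test and does not label these comparisons exploratory.

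Other parts of the synopsis bear on how sparse the data may be:

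- Enrollment is 70 subjects.
- General inclusion criterion 3 is "Patient presenting a score from 2 to 4 following Rutherford classification", so Rutherford can form up to three strata.
- The angiographic inclusion criteria list five lesion patterns, two of type C and three of type D.
- Secondary endpoint 4 is "Amputation rate at 1-, 6-, 12-, 24-, 36-, 48- and 60 month follow-up, defined as any amputation above the knee".

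**The concern.** The usual log-rank p-value refers the statistic to a chi-square distribution. That approximation needs a reasonable number of events and groups that are not too unequal. With very few events the statistic can take only a few values, and its tail probability may be far from the nominal one. The SAP applies a fixed 0.05 threshold to every such comparison without regard to this.

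At stake is the subgroup reporting. One chance event in a small stratum could be published as a significant risk factor. This is a property of each single test and is separate from how many tests are run. The primary patency estimate does not depend on it.

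**Working it through.** **Inputs from the documents.** n = 70; log-rank test; threshold 0.05, taken as two-sided because sidedness is not stated; up to three Rutherford classes. There is no power or sample-size calculation to reproduce.

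**Assumptions.** Stratum size m; number of events d; no censoring, so all 70 are at risk at the first event; event risk from 1% to 5% where sizes are averaged.

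**Step 1: one event in the trial, two groups.** Let s = m/70 be the stratum's share. If the event falls in the stratum, observed minus expected is 1 − s and the variance is s(1 − s), so

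chi-square = (1 − s)²/[s(1 − s)] = (1 − s)/s.

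Under the null the event falls in the stratum with probability s. For s below 0.5 that is also the exact p-value.

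| m | chi-square | log-rank p | exact p = m/70 |
|---|---|---|---|
| 3 | 22.33 | <0.0001 | 0.043 |
| 4 | 16.50 | <0.0001 | 0.057 |
| 7 | 9.00 | 0.0027 | 0.100 |
| 10 | 6.00 | 0.0143 | 0.143 |
| 14 | 4.00 | 0.0455 | 0.200 |
| 15 | 3.67 | 0.0555 | 0.214 |

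The log-rank p is below 0.05 when (1 − s)/s exceeds 3.84, that is when s < 1/4.84 = 20.65%, or m ≤ 14. The exact p is below 0.05 only for m ≤ 3. The two disagree about significance from m = 4 to m = 14.

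**Step 2: conditions on the cut-off of 14.**

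- Three groups (2 degrees of freedom, critical value 5.99): 70/6.99 gives m ≤ 10. At m = 10, chi-square is 6.00 and p = 0.0498.
- Fewer at risk: with 60, 50 or 40 still at risk, the two-group cut-off is 12, 10 or 8 at risk in the stratum.
- A second event outside the stratum: m = 14 then gives p = 0.27 to 0.29, depending on order. Significance needs m ≤ 6, or m = 7 if the stratum's event comes first (p = 0.048).

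**Step 3: true size given the number of events.** This is a full enumeration of the two-group statistic under the null, with sequential risk sets.

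| Events d | m = 14 | m = 35 |
|---|---|---|
| 1 | 20.0% | 0% |
| 2 | 3.8% | 0% |
| 3 | 10.0% | 0% |
| 4 | 2.3% | 11.4% |
| 5 | 5.1% | 5.4% |
| 10 | 2.3% | 8.2% |

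The size moves up and down with d rather than settling on one side of 5%. At 20 and 30 events (simulation, 40,000 runs) it lies between 4.5% and 6.5% for strata of 3 to 35.

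**Step 4: size averaged over the number of events.** The event count is not known at planning, so the sizes are weighted by a binomial(70, q) distribution for d.

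| Event risk q | m = 14 | m = 35 |
|---|---|---|
| 1% | 7.8% | 0.1% |
| 2% | 9.2% | 0.5% |
| 3% | 8.6% | 1.4% |
| 5% | 6.7% | 3.5% |

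For strata of 7 and 10 the corresponding averages lie between about 4.8% and 6.7%.

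**The case against.** The case against has weight. The 20% figure is a peak: it needs exactly one event in the trial, two groups and the least favourable stratum size. A planned test does not condition on a known event count, and the averages in step 4 stay below 10%. In balanced strata with rare events the test is conservative, which is the opposite error. The analysis is mainly descriptive, and no primary conclusion rests on these comparisons. All of this stands. It limits the size of the problem, but the SAP still declares significance by a p-value that can be 0.0455 where the exact one is 0.20.

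A reader might infer three stronger points that the documents do not support.

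- *The log-rank test is invalid for every time-to-event endpoint here.* It is adequate with about 20 or more events, and loss of patency over 60 months could reach that. The documents give no rates either way.
- *Any planned test has two to four times the nominal error rate.* That is true only at particular combinations of stratum size and event count.
- *The confidence intervals fail in the same way.* The SAP says only "For all variables a 95% confidence interval for the relevant parameters of the underlying distribution will be calculated". It names no normal-approximation or other interval method, and exact intervals would comply.

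Rarity is also an assumption. It is plausible for above-knee amputation in Rutherford 2 to 4 patients, and less certain for stent graft occlusion. Amputation is defined as a rate at visits, so including it among the time-dependent events is a reasonable reading but not an explicit statement.

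**Conclusion.** The point holds for sparse endpoints and small strata. There, the SAP's rule does not deliver the 5% error rate it implies: depending on stratum size and event count, the size runs from 0% to 20% in the cases checked. For a planned test at assumed event risks of 1% to 5%, the inflation is moderate for a stratum of 14 (about 7% to 9%), and with equal halves the test is conservative (below 4%). These figures assume two groups and no censoring. The effect is confined to subgroup claims, so it is a modest defect, worth correcting because the correction is cheap.

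**What to change.** Add two sentences to the SAP. First, p-values for comparisons between strata come from the exact or permutation distribution of the log-rank statistic. Second, endpoints with very few events, for example fewer than about 5 in total, are listed individually without a p-value. The second sentence is needed because for strata of 1 to 3 patients a single event gives an exact p of 1/70 = 0.014 to 3/70 = 0.043, which is still below 0.05. The threshold of 5 is a judgement and should be fixed before the data are examined. Labelling the stratified p-values exploratory would also help.

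The cost is small: standard software does this, and neither data collection nor trial conduct changes. The downside is that fewer subgroup results will be called significant.
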